### 6.6.3 Completed Cases Population

The Completed Cases (CC) population will include all ITT subjects who complete 30-day follow-up. The CC population will also include ITT subjects who experience failure of the primary effectiveness endpoint prior to the beginning of the 30-day follow-up timepoint, irrespective of their length of follow-up.

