#### 7.6 Subject Level and Lesion Level Analyses

The ITT dataset will be used for all safety endpoints. Each safety-related endpoint will be assessed on a subject-level basis; expressed as the number of subjects experiencing at least one event divided by the number of subjects with evaluable observations.

The CC dataset will be used for all effectiveness endpoints. Categorical effectiveness endpoints will be expressed as the number of Target Lesions meeting the effectiveness criteria divided by the number Target Lesions with evaluable observations. Continuous effectiveness endpoints will be assessed with mean or median and standard deviation or range, as appropriate for the distribution of data. Certain

effectiveness endpoints will be assessed on a lesion-level basis; for example, the primary effectiveness endpoint of Clinical Success. Other effectiveness endpoints will be assessed at the subject level; for example, measures related to resource utilization including procedure duration, contrast volume administered, and fluoroscopy time.

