## 8.8 Withdrawals and Loss to Follow-Up

m If an in-window telephone visit prompts an in-person visit that, for scheduling reasons, cannot not performed within the 30-day window, no protocol deviation will be reported. Any abnormalities detected at a late 30-day in-person visit will be assigned to the 30-day visit timepoint.

Study participation is completely voluntary, and each subject is free to withdraw from the study at any time. An investigator also has the right to withdraw the subject from the study in the event of reasons concerning the health or well-being of the subject, or in the case of lack of cooperation. Should a subject decide to withdraw for any reason, or should the investigator decide to withdraw the subject, all efforts will be made to complete and report the observations up to the time of withdrawal as thoroughly as possible. A complete, final evaluation at the time of the subject's withdrawal must be made and an explanation given as to why the subject is withdrawing or being withdrawn from the study.

The reason for and date of withdrawal must be recorded on the subject's End of Study eCRF. If the reason for the withdrawal is a device- or procedure-related AE, the event must be reported to the Sponsor and recorded on the eCRF.

If the procedure is aborted, the subject does not need to complete the follow-up assessments, unless the subject is converted to surgical repair. The subject's enrollment roster position will not be made available to other subjects.

If a subject dies during the course of the study, the Sponsor will request an autopsy provided the subject authorized an autopsy in the event of death during the course of the study. Autopsy observations should include documentation of condition of body organs and determination of device and/or procedure relationship to death.

All efforts will be made to retain subjects in order to collect data at the 30-day the follow-up visit. Due diligence in reaching the subject must be made by:

- Two documented telephone contact attempts, emails, or regular postal mail letters; and
- A certified letter

After the above attempts were made, if no response is obtained, the final evaluation of a given subject will be the last visit at which study-related procedures were performed on that subject. The End of Study eCRF page will need to be completed and communication attempts must be documented.

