1. Technical Success, defined as absence of angiographic evidence of bleeding from the target lesion at the conclusion of the index procedure;
2. Successful delivery of Lava and intact retrieval of the microcatheter;
3. Assessment of each element of the primary safety endpoint (MAE) as an individual component within 30 days of the index procedure;
4. Symptomatic ischemia in the target territory that does not require intervention within 30 days of the index procedure;
5. All-cause mortality within 30 days of the index procedure;
6. Bleeding-related mortality (attributable to bleeding in a target territory) within 30 days of the index procedure;
7. Open surgical conversion for persistent or recurrent bleeding within 30 days of the index procedure;
8. Device-related serious adverse events within 30 days of the index procedure;
9. Procedure-related serious adverse events within 30 days of the index procedure;

 The effectiveness endpoint is lesion-based and not subject-based. Failure of the effectiveness endpoint is triggered by events that are referable to the specific lesion and not to other events referable to another lesion in the same subject. For example, if a subject has two lesions where the first is treated successfully but the other rebleeds and requires emergency surgery, effectiveness would have been achieved in the first lesion but not in the second.

 Core laboratory-determined assessment of bleeding is used for the primary and secondary endpoints. If core laboratory images are unavailable or uninterpretable, the site-reported determinations will be used.

10. Access site hematoma (>5cm in longest axis) within 30 days of the index procedure;
11. Access site false aneurysm within 30 days of the index procedure;
12. Units of red blood cells transfused after administration of Lava;
13. Duration of the index procedure, total and after administration of Lava;
14. Contrast administered the during index procedure;
15. Fluoroscopy time during the index procedure;
16. Length of stay in the intensive care unit after the index procedure;
17. Length of hospitalization, total and after the index procedure.

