### 3.3 POPULATIONS FOR ANALYSES

The intention to treat (ITT) dataset, defined as all consented subjects in whom the Lava LES study device entered the vasculature irrespective of adherence with the entry criteria, treatment received, subsequent withdrawal, or deviation from the protocol, will be used for all safety endpoints. Each safety-related endpoint will be assessed on a subject-level basis; expressed as the number of subjects

experiencing at least one event divided by the number of subjects with evaluable observations (see 3.4.1 handling of missing data).

The complete cases (CC) dataset, defined as all ITT subjects who complete 30-day follow-up, will be used for all effectiveness endpoints. Categorical effectiveness endpoints will be expressed as the number of Target Lesions meeting the effectiveness criteria divided by the number Target Lesions with evaluable observations (completed 30-day follow-up). Certain effectiveness endpoints will be assessed on a lesion-level basis; for example, the primary effectiveness endpoint of Clinical Success. Other effectiveness endpoints will be assessed at the subject level; for example, measures related to resource utilization including procedure duration, contrast volume administered, and fluoroscopy time.

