### **Handling of Missing Data**

All attempts will be made to limit the amount of missing data. For all analyses of the primary endpoints, the number of observations available will be reported so the reader can assess the impact of missing data. In general, and for the primary endpoint analyses, missing data will not be imputed and analyses will be based on available data. For missing values on the primary safety endpoint, an adjustment to the denominator will be made based on the amount of evaluable data. For each visit (or reporting time point), the occurrence rate will be calculated as the number of subjects with certain endpoint occurrence term over the number of evaluable subjects. The evaluable subjects at each reporting time point include all subjects who are enrolled by the snapshot date and

- 1) had an endpoint occurrence within (on or before) the reporting cutoff days (30 days), or
- 2) had a follow-up at or after the lower limit of the reporting window (23 days), or
- 3) the withdrawal consent date/recorded lost-to-follow-up date at or after the lower limit of the reporting window.

Sensitivity analyses will be performed to assess the impact of missing data and potential correlation in the data for the primary endpoints. Three different sensitivity analysis are planned: (1) As described in the protocol, Target Lesions with unavailable effectiveness data will be assumed to have missing data at random and will be imputed by random selection with replacement of data from Target Lesions with complete data. (2) A tipping point analysis will be conducted in which lesions or subjects censored without an event prior to 30 days follow-up are sequentially imputed as failures at the time of censoring. (3) A generalized estimating equation (GEE) logistic regression model will be used to estimate clinical success taking into account potential correlation of multiple Target Lesions within a subject using an exchangeable working correlation structure. The analyses for all the secondary endpoints will not include imputation for missing data, and no formal statistical hypotheses will be tested.

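### Procedure duration, contrast volume, fluoroscopy time and, by its nature, Technical Success are known when the index procedure ends, yet the plan summarises them in Completed Cases and so leaves out subjects without 30-day follow-up.

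*SAP*

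**What the plan says.** SAP 3.3 assigns all safety endpoints to the ITT set. The Completed Cases set, "defined as all ITT subjects who complete 30-day follow-up, will be used for all effectiveness endpoints". For categorical effectiveness endpoints, the number of successful lesions is "divided by the number Target Lesions with evaluable observations (completed 30-day follow-up".

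Protocol 7.6 also uses Completed Cases for all effectiveness endpoints. Both sections give as examples of subject-level effectiveness endpoints "measures related to resource utilization including procedure duration, contrast volume administered, and fluoroscopy time".

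Two further procedural endpoints are listed in SAP 2 and Protocol 5.3: "Technical Success, defined as absence of angiographic evidence of bleeding from the target lesion at the conclusion of the index procedure", and "Successful delivery of Lava and intact retrieval of the microcatheter". Neither document labels these two as safety or effectiveness, and SAP 3.4.3, on secondary endpoints, names no analysis set.

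The two documents define Completed Cases differently. Protocol 6.6.3 goes beyond completers: "The CC population will also include ITT subjects who experience failure of the primary effectiveness endpoint" before the 30-day timepoint, whatever their length of follow-up. SAP 3.3 has no such sentence.

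Protocol 8.8 adds: "If the procedure is aborted, the subject does not need to complete the follow-up assessments, unless the subject is converted to surgical repair". On missing data, SAP 3.4.1 says: "The analyses for all the secondary endpoints will not include imputation for missing data, and no formal statistical hypotheses will be tested".

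**The concern.** Procedure duration, contrast volume, fluoroscopy time and Technical Success need no follow-up. Restricting them to subjects with 30-day status conditions a day-0 result on later survival and retention, and leaves observed values out of the summary.

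That matters if the omitted subjects differ from the rest, and the documents give one concrete reason why they might. A subject whose procedure is aborted after the device has entered the vasculature is in ITT, but Protocol 8.8 excuses that subject from follow-up unless converted to surgical repair. Such a case could well be a technical failure, and it can leave Completed Cases because the protocol did not ask for the visit. Nothing offsets the loss: secondary endpoints are not imputed, and the missing-data sensitivity analyses in SAP 3.4.1 are planned for the primary endpoints.

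At stake is the accuracy of the reported procedural results of a pivotal device study. The primary tests are not at stake.

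**Working it through.** **Step 1. Sizes of the two sets.** Inputs from SAP 3.2 and Protocol 7.9: goal 72%, anticipated success 84%, one-sided alpha 0.025, exact binomial test, 80% power, 10% attrition.

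- Exact test at n = 101: reject at 82 or more successes, attained alpha 0.0227, power 81.9%. At n = 97 power is 79.8%. The plan's 101 is reproduced.
- Attrition: 101 / 0.90 = 112.2, rounded up to 113. The plan's 113 is reproduced.
- Expected without 30-day status: 113 − 101 = 12 subjects, and 12 / 113 = 10.6%.

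**Step 2. Who is left out under each definition.**

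| ITT subject without 30-day follow-up | SAP 3.3 | Protocol 6.6.3 |
|---|---|---|
| Early primary-effectiveness failure | left out | kept |
| Early death without effectiveness failure | left out | left out |
| Withdrawal or loss to follow-up, no failure | left out | left out |
| Aborted procedure excused from follow-up, no failure recorded | left out | left out |

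Neither document says that a death before day 30 without a bleeding failure counts as completing follow-up; the table assumes that it does not.

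**Step 3. Effect on a day-0 rate.** Let m of 113 be left out, with success rate pC in those analysed and pN in those left out. Then

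Completed Cases rate − ITT rate = (m / 113) × (pC − pN).

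The sign depends on whether pN lies below or above pC. The documents give neither rate, so the following is an illustration. It assumes one lesion per subject and 96/101 = 95.0% in completers.

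| Successes among the 12 left out | ITT rate | Completed Cases minus ITT |
|---|---|---|
| 0 | 96/113 = 85.0% | +10.1 points |
| 6 | 102/113 = 90.3% | +4.8 points |
| 9 | 105/113 = 92.9% | +2.1 points |
| 12 | 108/113 = 95.6% | −0.5 points |

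Other attrition, with pC = 95% and pN = 50%: 6 of 113 left out gives (6/113) × 45 = 2.4 points; 17 of 113 gives (17/113) × 45 = 6.8 points.

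**Step 4. Where technical failures go under the protocol.** Protocol 18 defines persistent bleeding as bleeding at the final index-procedure angiogram, which is the opposite of Technical Success. It also states that continued bleeding is a failure of the effectiveness endpoint. On that reading technical failures stay in the protocol's Completed Cases, those left out are all technical successes, and only the last row of the table applies: 95.0% reported against 95.6%. Protocol 5.2 is narrower. It requires BARC Type 3 or greater bleeding after the index procedure, so a technical failure need not be an effectiveness failure. The documents do not settle which reading governs.

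**Step 5. Precision.** √(113/101) = 1.058, so the standard error is about 6% larger in Completed Cases. That is minor; selection is the main issue.

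**The case against.** The strongest reply is that the protocol already protects against the selection that would matter most. Early effectiveness failures stay in Completed Cases, fatal target-lesion bleeding is an endpoint failure (BARC Type 5), and on the Protocol 18 definitions technical failures stay too. The SAP might also be read as shorthand for the protocol's set. This stands in part: it narrows the loss under the protocol and can reverse the sign for Technical Success. It does not help procedure duration, contrast volume or fluoroscopy time, which are left out whenever the subject is left out. Nor does it repair the SAP, whose written definition omits the early failures.

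A second reply is that Technical Success and delivery with intact retrieval are nowhere labelled effectiveness. For Technical Success this carries little weight: it measures bleeding control by lesion, and no other set is offered. For delivery and retrieval it stands. That endpoint overlaps the safety components catheter breakage and catheter entrapment, and could already belong to ITT.

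A third reply is that nothing is lost from the record, because SAP 3.4.8 lists individual data and SAP 3.4.1 reports the number of evaluable observations for continuous measures. That is true, but a listing does not correct a summary rate or mean.

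A reader might infer that Technical Success will be overstated by about 5 points, and procedure time and contrast understated. The documents do not support this. The 5 points require an assumed 50% success rate among those left out, and no document gives a rate for either group or says that difficult procedures predict dropout.

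**Conclusion.** The point holds as a defect in the choice of analysis set. It is explicit for procedure duration, contrast volume and fluoroscopy time, and a sound reading for Technical Success. For delivery and intact retrieval the plan is silent rather than wrong.

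At the planned attrition about 12 of 113 subjects (10.6%) would be missing from these summaries under the SAP's wording, and fewer under Protocol 6.6.3 if some of the 12 are early effectiveness failures. The direction and size of any bias are unknown. The span of 85.0% to 95.6% for the all-ITT Technical Success rate rests on an assumed 96/101 in completers and one lesion per subject; up to four lesions are allowed, so lesion counts may differ. The excuse from follow-up after aborted procedures makes informative loss plausible but does not demonstrate it.

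Only descriptive secondary endpoints are affected. Study success, alpha and power do not change. The change is still worth making, because it uses data already collected.

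**What to change.** 1. In SAP 3.3 and Protocol 7.6, state that endpoints determined by the end of the index procedure (Technical Success, procedure duration, contrast volume, fluoroscopy time) are summarised in all ITT subjects, or all their Target Lesions, with an observed value.
2. Assign successful delivery with intact microcatheter retrieval explicitly to ITT.
3. Keep Completed Cases for endpoints that need 30-day status, and name the analysis set for each secondary endpoint in SAP 3.4.3.
4. Align the SAP's Completed Cases definition with Protocol 6.6.3, so that early effectiveness failures are kept in both documents.

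The cost is a few sentences in the two documents. No new data, no extra subjects and no change to the primary tests are needed.

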## 3.4 STATISTICAL ANALYSES

### 3.4.1 GENERAL APPROACH

Except where otherwise specified, the following general principles apply to the planned statistical analyses. All statistical analysis will be conducted using {SAS version 9.4 or later (SAS Institute Inc., Cary, NC)} or other widely accepted statistical or graphical software as required.

#### **Descriptive Statistics**

Continuous data will be summarized with mean, standard deviation, median, minimum, maximum, and number of evaluable observations. Categorical variables will be summarized with frequency counts and percentages. Confidence intervals may be presented, where appropriate, using the t-distribution for continuous data and exact binomial method for categorical variables.

#### **Study Visit**

Study visit Day 0 is the date of the index procedure. Days in study will be calculated relative to the index procedure as follows:

Study Days = Assessment Date – Index Procedure Date

For each subject, duration in study will be based on last study contact date which is the latest date of all follow-up visits, assessments, adverse event onset or resolution, and study exit including date of death.

Duration variables will be calculated as follows:

Duration Days = End Date – Start Date

#### **Visit Windows**

Unless otherwise specified, visit assessments will be analyzed for each analysis time point according to the visit entered in the electronic Case Report Form (eCRF).

#### **Statistical Significance**

Unless otherwise specified, hypothesis testing will be performed at the two-sided 0.05 significance level. P-values will be rounded to three decimal places. If a p-value is less than 0.001 it will be reported as "<0.001". If a p-value is greater than 0.999, it will be reported as ">0.999".

### **Reporting Precision**

Unless otherwise specified, the following conventions will apply for data display. In general, percentages will be displayed to 1 decimal place. Percentages <0.05% will be reported to 2 decimal places. For continuous parameters, means and medians will be reported to 1 additional decimal place than the measured value while standard deviation will be reported to 2 additional decimal places than the measured value. Minimum and maximum values will be reported to the same precision as the measured value.

### **Handling of Missing Data**

All attempts will be made to limit the amount of missing data. For all analyses of the primary endpoints, the number of observations available will be reported so the reader can assess the impact of missing data. In general, and for the primary endpoint analyses, missing data will not be imputed and analyses will be based on available data. For missing values on the primary safety endpoint, an adjustment to the denominator will be made based on the amount of evaluable data. For each visit (or reporting time point), the occurrence rate will be calculated as the number of subjects with certain endpoint occurrence term over the number of evaluable subjects. The evaluable subjects at each reporting time point include all subjects who are enrolled by the snapshot date and

- 1) had an endpoint occurrence within (on or before) the reporting cutoff days (30 days), or
- 2) had a follow-up at or after the lower limit of the reporting window (23 days), or
- 3) the withdrawal consent date/recorded lost-to-follow-up date at or after the lower limit of the reporting window.

Sensitivity analyses will be performed to assess the impact of missing data and potential correlation in the data for the primary endpoints. Three different sensitivity analysis are planned: (1) As described in the protocol, Target Lesions with unavailable effectiveness data will be assumed to have missing data at random and will be imputed by random selection with replacement of data from Target Lesions with complete data. (2) A tipping point analysis will be conducted in which lesions or subjects censored without an event prior to 30 days follow-up are sequentially imputed as failures at the time of censoring. (3) A generalized estimating equation (GEE) logistic regression model will be used to estimate clinical success taking into account potential correlation of multiple Target Lesions within a subject using an exchangeable working correlation structure. The analyses for all the secondary endpoints will not include imputation for missing data, and no formal statistical hypotheses will be tested.

More generally, in the case of partial adverse event onset date or date of death, the unknown portion of the date of the event will be imputed. If the month and year are known, the 1st of the month will be used for analysis. If only the year is known, the event will be analyzed as if it occurred on June 30th of the known year. In the rare case that the date is fully unknown, the date will be imputed as the initial treatment date. Imputation of partial dates is subject to the condition that it

must occur on or after the initial treatment date. In the case where the imputed date is prior to the initial treatment date, the date of the initial treatment will be used. As death cannot occur before any documented subject contact, for date of death the imputed date of death must occur on or after last known contact in study.

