## 7.7 Missing or Incomplete Data

Every effort will be made to minimize the amount of missing data. Recognizing the difficulty of avoiding some missing data, however, data imputation methods with sensitivity imputation analyses will be carried out. Safety endpoint analyses will include all subjects experiencing at least one component of the safety endpoint or with follow-up to the lower limit of the follow-up window for the 30-day time point (i.e., the denominator will be adjusted for missing data). Target Lesions with unavailable effectiveness data will be assumed to have missing data at random and will be imputed by random selection with replacement of data from Target Lesions with complete data. The robustness of the multiple imputation outcome will be tested with a tipping point analysis encompassing all possible imputation outcomes.

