## 8.5 Follow-Up Assessment

A 30-day follow-up visit will be performed; with a visit window between 23 and 37 days. The visit may be done via telephone. Any abnormalities will prompt an in-person visit.m Selected baseline medications (anticoagulants, antiplatelets) will be recorded. Adverse events will be recorded, as will any red blood cell transfusions between discharge and the 30 days. An arterial duplex ultrasound examination will be required for abnormalities at the access site (hematoma, mass, diminished peripheral pulses, thrill or bruit) and a venous duplex study will be performed for leg edema or other signs suggestive of deep venous thrombosis or venous injury.

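### A follow-up from day 23 is enough to score a 30-day primary endpoint as event-free, so days 24-30 may rest on passive reporting alone

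*SAP*

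**What the plan says.** - **Endpoints.** Protocol 5.1, 5.2 and 7.2 and SAP section 2 define freedom from MAE and Clinical Success over 30 days from the index procedure.
- **Safety evaluability.** SAP 3.4.1 introduces its rule with "For missing values on the primary safety endpoint, an adjustment to the denominator will be made based on the amount of evaluable data". A subject is evaluable on any one of three grounds. The first is that the subject "had an endpoint occurrence within (on or before) the reporting cutoff days (30 days". The second is that the subject "had a follow-up at or after the lower limit of the reporting window (23 days". The third is a consent-withdrawal date or recorded lost-to-follow-up date on or after that same lower limit. Protocol 7.7 likewise admits event-free subjects "with follow-up to the lower limit of the follow-up window for the 30-day time point".
- **Visit.** Protocol 8.5: "A 30-day follow-up visit will be performed; with a visit window between 23 and 37 days". The visit may be by telephone. It is the only scheduled contact after discharge.
- **Visit assignment.** SAP 3.4.1, Visit Windows: "visit assessments will be analyzed for each analysis time point according to the visit entered in the electronic Case Report Form (eCRF". Study day plays no part in the default rule.
- **Effectiveness set.** SAP 3.3 has Completed Cases "defined as all ITT subjects who complete 30-day follow-up". Protocol 6.6.3 agrees and adds subjects who failed earlier. Neither gives a minimum day.
- **Sensitivity analysis.** SAP 3.4.1 includes a tipping-point analysis that imputes failure for lesions or subjects censored event-free before 30 days.

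**The concern.** The endpoint closes on day 30, but the rule for calling a subject event-free closes on day 23. A subject who is well on a day-23 call enters the safety denominator as a 30-day success with seven days not covered by any contact. No passage in either document asks the site to call again.

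For effectiveness the route is indirect. The day-23 rule is written for safety. But a visit on day 23 is in window, it is labelled the 30-day visit in the eCRF, and analysis follows the label. It would therefore appear to satisfy the follow-up condition for Completed Cases.

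The third evaluability ground has the same weakness, possibly in a sharper form. It looks at the date on which loss to follow-up was recorded, not the date the subject was last known to be event-free. A subject last seen at discharge and recorded as lost on day 25 would count as evaluable.

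There is no control arm to share the error. Success is judged against fixed goals of 72% and 82%, so an event missed in this way counts wholly in the device's favour, and how often it can happen depends on when sites schedule their calls.

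**Working it through.** **The plan's own figures.** With an exact one-sided test at 0.025 and n = 101:

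- Effectiveness needs 82 successes (exact lower limit 72.2%; 81 gives 71.1%). The exact size at 72% is 2.27% and the power at 84% is 81.9%. The stated 101 and, after 10% attrition, 113 both reproduce.
- Safety needs 91 successes (exact lower limit 82.5%; 90 gives 81.3%). The exact size at 82% is 1.81% and the power at 92% is 81.6%.

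**Inputs not in the documents (assumptions).** These are the timing of contacts within days 23-37, the timing of events within 30 days, and the share of late events that reach the site without a contact. The calculation below takes that last share as zero.

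**Unobserved share u.** If contacts fall evenly on the 15 days from 23 to 37, then 7 of 15 (47%) fall before day 30. The mean number of unobserved days is (7+6+5+4+3+2+1)/15 = 28/15 = 1.87. If events are even over 30 days, u = 1.87/30 = 0.0622.

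**Apparent success rate** = 1 − (1 − p)(1 − u), where p is the true 30-day rate. The chance of passing is the binomial probability of reaching 82 or 91 of 101 at the apparent rate.

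| Scenario, true rate at the goal | u | Effectiveness (72%): apparent rate, chance of passing | Safety (82%): apparent rate, chance of passing |
|---|---|---|---|
| Status known at day 30 | 0 | 72.0%, 2.3% | 82.0%, 1.8% |
| Even contacts, half the late-event share | 0.0311 | 72.9%, 3.5% | 82.6%, 2.5% |
| Even contacts, even events | 0.0622 | 73.7%, 5.3% | 83.1%, 3.5% |
| Every contact on day 23, even events (extreme bound) | 0.2333 | 78.5%, 30% | 86.2%, 16% |

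**Safety, allowing for the event mix.** Protocol 7.8.1 builds its composite from 4% ischemia, 2.5% non-target embolization and 1% for each of three other components: 4 + 2.5 + 3 = 9.5 points. Non-target embolization, catheter breakage and catheter entrapment arise in delivering Lava, and allergic reaction is tied to that exposure. If only ischemia can arise late, the late-capable share is 4/9.5 = 42% and u = 0.0622 × 0.42 = 0.0262. The apparent rate is then 82.5% and the chance of passing 2.4%. The every-contact-on-day-23 bound becomes 5.0%.

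**At the planned rates** (even contacts, even events), 84% effectiveness would read as 85.0% (0.16 × 0.0622 = 1.0 point) and 92% safety as 92.5% (0.08 × 0.0622 = 0.5 point).

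**The case against.** The strongest reply is that events on days 24-30 are not ignored. Protocol 10.2 requires all adverse events during the study to be reported, Protocol 8.6 provides unscheduled visits for rebleeding and complications, and the first evaluability ground counts any known event to day 30 whatever the contact date. An effectiveness failure is BARC Type 3 or greater bleeding or a reintervention, which leaves a medical record. Visits on days 30-37 cover the whole period. All of this stands. It limits the gap to subjects last contacted on days 23-29 and to events that the site does not learn of, for example a rebleed treated elsewhere. It does not close it.

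The timing assumptions also favour a larger effect. Most safety components are tied to the procedure, and persistent bleeding is defined at the final index angiogram, so some effectiveness failures may be fixed on day 0. This stands too, and is why the safety figure is given as a range.

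The tipping-point analysis might be thought to cover the problem. It is a sensitivity analysis without a pass criterion, and it does not say whether a subject who is evaluable on a day-23 contact counts as censored.

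Two stronger readings are tempting. One is that both rates are biased upward overall. That is not shown: Protocol 6.6.3 keeps early effectiveness failures in Completed Cases and drops early event-free losses, which pushes the other way. The other is that the footnote to Protocol 8.5, "Any abnormalities detected at a late 30-day in-person visit will be assigned to the 30-day visit timepoint", contradicts the SAP's day-30 cut-off for something found on, say, day 35. It does not. The footnote covers an in-person visit that could not be held within the window, so after day 37, and it labels a visit where the SAP dates an event.

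**Conclusion.** The mismatch is real. A 30-day endpoint is paired with a day-23 floor for being counted event-free. That floor is explicit for safety. For effectiveness it is inferred from the visit window, the eCRF labelling and the absence of any minimum day for completing follow-up. Taken alone, the rule can only raise the observed success rates.

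The size is modest and rests on assumptions. With even contacts, even events and no passive capture, the chance of passing at the goal goes from 2.3% to 5.3% for effectiveness, and from 1.8% to between 2.4% and 3.5% for safety. At the lower safety figure the 0.025 level is not exceeded. Events that cluster early, or passive capture, reduce all of these. The 30% and 16% figures need every contact on day 23 and should not be used to judge importance.

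The supportable conclusion is that the one-sided 0.025 level is not assured for the 30-day endpoints as defined, most clearly for effectiveness. Neither a breach of that level nor a net upward bias has been demonstrated. The change is worth making because the gap is avoidable at little cost.

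**What to change.** 1. In SAP 3.4.1 (second and third evaluability grounds) and Protocol 7.7, count a subject as evaluable only with an endpoint event by day 30 or known event-free status at day 30 or later. A recorded lost-to-follow-up date should not be enough by itself.
2. Apply the same rule to Completed Cases in Protocol 6.6.3 and SAP 3.3, so that completing 30-day follow-up has a stated minimum day.
3. Set the contact window to days 30-37, or keep days 23-37 and require one further call on or after day 30 to anyone reached on days 23-29.
4. State that subjects not reached again are treated as censored before day 30 in the tipping-point analysis.
5. Classify endpoint events by onset date, with day 30 as the cut-off in both documents.

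The cost is wording in two documents, a short repeat call for some subjects, and a few more non-evaluable subjects. In Completed Cases those would be event-free subjects dropped while early failures stay, which is why item 4 matters. The sample size stays at 101 and 113.
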